#### **9. Safety Analysis**

The safety profile is based on the incidence of Treatment Emergent Adverse Events (TEAEs) including DLTs and Serious Adverse Events (SAEs), as well as the change from baseline in standard clinical laboratory assessments, physical examination findings, vital signs, and 12-lead ECG recordings and will be summarized descriptively.

##### **9.1. Adverse Events**

Any AEs that occur from the time the initial Informed Consent Form (ICF) is signed by a participant until the end of study visit. This includes events occurring during the screening phase of the study and regardless of whether FLT201 is administered.

For a full definition of AEs for this study, see the protocol.

### **9.1.1. Treatment Emergent Adverse Events**

A TEAE is defined as an AE that meets any of the following conditions:

- begins during or after the infusion
- begins before the infusion and worsens in severity during or after the infusion
- is completely missing an onset date and end date
- is completely missing an onset date and the end date is on or after the date of infusion

All adverse events will be classified by SOC and preferred term according to MedDRA (Version 26.1 or higher).

An overview summary of the number and percentage of participants with any AE, any TEAE, serious TEAE, non-serious TEAE, IMP-related TEAE, IMP-related serious TEAE, TEAE leading to treatment discontinuation, and AE leading to death will be provided by study part, dose cohort, and overall. This summary will also be used for Lay Person summary part of the EU CTR reporting. A listing for all AEs will also be presented.

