15.3 Analysis of Primary Safety Endpoints

Dose-limiting Toxicities

All DLTs will be summarised by cohort/dose level.

Although the dose escalation is based on an algorithm, the final data may be used, for example, to model the DLTs as a function of dose, adjusted for any potential confounders, to further refine any estimate of the MTD (e.g., to determine the probability of toxicity closest to a given threshold toxicity at some observed dose level). The uncertainty around the estimate of the true DLT rate may be provided in terms of 95% confidence intervals or 95% credible intervals.

Adverse Events

Frequency of treatment-emergent AEs and SAEs will be calculated for each body system and preferred term, and by dose level, for number of events and number of participants reporting the event. The severity of the AEs and the relationship to study medication will be summarised for each body system and preferred term by cohort/dose level.

Other Safety Endpoints

Safety endpoints including the following will be summarized descriptively by cohort/dose level.

- Change from baseline in laboratory data
- Change from baseline in 12-lead ECG data
- Change from baseline in physical examination data
- Change from baseline in vital signs data.

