**Table 2-1 Primary Objective and Endpoints - Safety**

Primary Objective	Primary Endpoints
To assess the safety and tolerability of a single IV administration of FLT201 in adults with Gaucher disease type 1 (previously treated and previously untreated).	
Primary safety variable: incidence of TEAEs (including DLTs) from Day 1 to the last follow-up visit.
 
Other safety endpoints: incidence of AEs, SAEs, and changes from baseline in vital signs, 12-lead ECG, physical examination, and laboratory assessments from Day 1 to the last follow-up visit.

Abbreviations: AE=adverse event; DLT=dose-limiting toxicity; ECG=electrocardiogram; IV=intravenous; SAE=serious adverse event; TEAE=treatment emergent adverse event.
	

Table 2-2 presents the secondary objectives and endpoints.

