### **9.1.2. Relationship of Adverse Events to Investigational Medicinal Product**

The investigator will determine whether there is a reasonable causal relationship between the occurrence of the AE and exposure to IMP (FLT201) and non-investigational medicinal products (NIMP) (prednisolone/prednisone, methylprednisolone, and tacrolimus). If there is no valid reason for suggesting a relationship, then the AE should be classified as “Not Related.” Otherwise, if there is any valid reason for suspecting a possible cause-and-effect relationship between the IMP/NIMP and the occurrence of the AE, then the AE should be considered “Related.”

If the relationship to IMP/NIMP information is missing, then the corresponding AE is assumed to be related with reasonable possibility to the IMP/NIMP. If a participant experiences more than one occurrence of the same AE, the occurrence with the most-related relationship to IMP/NIMP will be used in summary tables.

The relationship of AEs to IMP/NIMP will be summarized by SOC, PT, study part, dose cohort, and overall.

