### **9.1.3. Severity of Adverse Event**

A summary of TEAEs by severity will be presented in a table. The severity that will be presented represents the most extreme severity captured on the eCRF page. The possible severities are measured on the CTCAE scale which goes from 1 to 5 where 1=‘mild’, 2=‘moderate’, 3=‘severe’, 4=‘life-threatening’ and 5=‘fatal’.

The severity of the AEs will be summarized by SOC, preferred term, study part, dose cohort, and overall. SOC and preferred terms within SOC will be presented by descending frequency based on overall count. If a participant reports more than one AE within the same preferred term, the AE with the maximum severity will be presented. If a participant reports more than one AE within the same SOC, then the participant will be counted only once with the maximum severity at the SOC level. If severity is missing, then Grade 3 “Severe” is assumed.

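### SAP 9.1 leaves out the event counts that protocol 15.3 requires for TEAEs and SAEs by dose level, and SAP section 14 does not record the departure

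*SAP*

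**What the plan says.** The primary safety variable is "incidence of TEAEs (including DLTs) from Day 1 to the last follow-up visit" (SAP Table 2-1, matching protocol Table 3). Neither document defines incidence as events or as participants at that point.

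Protocol 15.3 settles the unit for the analysis. TEAE and SAE frequencies are to be calculated for each body system and preferred term "and by dose level, for number of events and number of participants reporting the event".

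The SAP is narrower:

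- 9.1.1: "An overview summary of the number and percentage of participants with any AE, any TEAE, serious TEAE", followed by further rows including related, treatment-discontinuation and fatal events. A listing of all AEs is added.
- 9.1.2: "The relationship of AEs to IMP/NIMP will be summarized by SOC, PT, study part, dose cohort, and overall". When the same AE recurs in a participant, only the most-related occurrence is used.
- 9.1.3: "The severity of the AEs will be summarized by SOC, preferred term, study part, dose cohort, and overall". "If a participant reports more than one AE within the same preferred term, the AE with the maximum severity will be presented"; for several AEs within one SOC, "then the participant will be counted only once with the maximum severity at the SOC level".
- 9.1.4 to 9.1.7 (DLTs, SAEs, non-serious TEAEs, AESIs): tables by SOC, preferred term and cohort, with no counting unit stated.
- 9.1.8: each participant is counted once.

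Protocol section 15 says that departures from its planned analyses will be detailed in the SAP. SAP section 14 lists four: CCL18, urinalysis, AEs leading to study discontinuation, and the interim analysis. Event counts are not among them.

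**The concern.** A programmer who follows the SAP as written would produce AE tables without a tabulation that the protocol requires for the primary safety variable, and nobody would have recorded a decision to leave it out.

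What is lost is recurrence. Protocol 14.2.9 makes a single ALT value above normal, in a participant normal at baseline, an AESI. Protocol 12.2.1 has liver tests taken two to three times a week. More than one ALT episode in a participant is therefore foreseeable. Under SAP 9.1.2 and 9.1.3, a participant with one episode and a participant with four give the same table entry if the worst grade and relationship are the same.

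The loss matters more because cohorts are very small. If nearly everyone has some TEAE, the any-TEAE percentage cannot separate the doses, and the number of events is one of the few simple summaries that still can.

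**Working it through.** **1. Counting unit, table by table**

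| Output | Protocol 15.3 | SAP |
|---|---|---|
| TEAEs by body system, term, dose | events and participants | participants (9.1.1 overview; 9.1.3 severity table) |
| SAEs by body system, term, dose | events and participants | unit not stated (9.1.5) |
| Relationship | summarised, unit not stated | one record per repeated AE (9.1.2) |
| Severity | summarised, unit not stated | one record per participant per term and per SOC (9.1.3) |
| DLTs, non-serious TEAEs, AESIs | DLTs summarised; no separate rule for the other two | unit not stated (9.1.4, 9.1.6, 9.1.7) |

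No SAP table commits to a number of events. The reference in 9.1.3 to overall count only sets the sort order.

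**2. When does the any-TEAE row stop being informative?**

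The documents give no expected TEAE rate, alpha or power, so there is no planned figure to reproduce. Part 1 has about 12 participants in about 4 cohorts, so 12 / 4 = 3 per cohort. The planned minimum is 2. One is possible under protocol 13.3.1.2, and more than 3 under 13.3.1.

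Let p be the chance that a participant has at least one TEAE (assumed, and taken as equal in all cohorts).

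- A cohort of n reads 100% with probability q = pⁿ.
- At least 3 of 4 cohorts read 100% with probability 4q³(1 − q) + q⁴.

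| p (assumed) | One cohort at 100%, n=2 / n=3 | At least 3 of 4 cohorts, n=2 / n=3 |
|---|---|---|
| 0.70 | 49% / 34% | 30% / 12% |
| 0.80 | 64% / 51% | 55% / 33% |
| 0.90 | 81% / 73% | 83% / 70% |
| 0.95 | 90% / 86% | 95% / 90% |
| 0.99 | 98% / 97% | 99.8% / 99.5% |

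Example for p = 0.90, n = 3: q = 0.9³ = 0.729, and 4 × 0.729³ × 0.271 + 0.729⁴ = 0.420 + 0.282 = 0.702.

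Most cohorts reading 100% therefore needs p of about 0.90-0.95 or more. If events per participant were Poisson with mean L, then p = 1 − exp(−L), so p = 0.90 needs L = −ln 0.10 = 2.3 and p = 0.95 needs L = −ln 0.05 = 3.0. Variation between participants weakens this. With gamma-Poisson counts of mean 3 and dispersion 0.5, the chance of no event is (1 + 0.5 × 3)⁻² = 0.16. Then p = 0.84, and a cohort of three reads 100% with probability 0.84³ = 59%.

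**3. Rarer categories do not saturate**

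At an assumed true rate of 0.33, a cohort of three reads 0/3 with probability 0.67³ = 30% and 3/3 with probability 0.33³ = 4%. Rows for related, severe or serious events, or for single terms, can therefore differ between doses. Precision is poor in any case: the exact 95% interval has lower limit 0.025^(1/n), giving 29%-100% for 3/3 and 16%-100% for 2/2.

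**4. Follow-up length**

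SAP 7.2.2 puts the end-of-study visit at Week 38 outside the US and Month 24 in the US, and SAP 9.1 collects AEs to that visit. Twenty-four months is about 104 weeks, and 104 / 38 = 2.7. At a constant rate, a US participant would contribute about 2.7 times as many events. Raw totals would mix dose with the regional make-up of each cohort.

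**The case against.** The strongest reply is that the SAP is silent on event counts and does not forbid them. SAP section 1 says it is to be read together with the protocols, the unit is unstated in 9.1.4 to 9.1.7, and the one-record rules in 9.1.2 and 9.1.3 say how to classify a participant. They do not rule out an events column. That is fair as far as it goes: this is an omission and not an explicit removal. But protocol section 15 makes the SAP the detailed description of all summaries and the place to record departures. Silence there leaves the required counts unspecified.

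A reader might infer that the primary endpoint has been reduced to whether a participant had any event, so that no dose pattern can show. The documents do not support this. The overview has several further rows. Separate tables by SOC, preferred term and cohort cover relationship, severity, DLTs, SAEs, non-serious TEAEs and AESIs. All AEs are listed, and SAP 9.6.1 plots ALT, AST and total bilirubin by participant over time, which for two or three people shows recurrent liver episodes well. A listing or plot is still not the by-dose tabulation in protocol 15.3.

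A reader might also want to state the loss as power to detect a dose effect. That does not fit: sample size rests on feasibility, all analysis is descriptive, and any such figure would depend on assumed event rates, an assumed dose effect and an assumed spread between participants.

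**Conclusion.** The point holds as an unrecorded departure from protocol 15.3 on the primary safety variable. The protocol requires events and participants for TEAEs and SAEs. The SAP specifies no events, counts per participant wherever it states a rule, and does not list the change in section 14. This part rests on the text alone.

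The consequence is moderate and conditional. Recurrent episodes of one term are indistinguishable from single ones in the tables with a stated rule. The any-TEAE row is likely to be near 100% in most cohorts only if about 90-95% or more of participants have a TEAE. That is plausible here but is not a figure in the documents. Dose differences can still appear descriptively in the other AE tables and the listing. The change should be made, because it is cheap and restores what the protocol promised.

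**What to change.** In SAP 9.1.1 to 9.1.7, show the number of events beside the number and percentage of participants, by SOC, preferred term and dose cohort. Protocol 15.3 requires this for TEAEs and SAEs. Extending it to related events, severity and AESIs is advisable. State the counting unit in 9.1.4 to 9.1.7, where none is given. The maximum-severity and most-related rules can stay for the participant columns.

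Show events over a common window from Day 1 to Week 38, and/or per unit of participant-time. This goes beyond protocol 15.3 and should be labelled as an addition. The common window is the safer choice if AEs cluster early, because a rate over 24 months would then be diluted.

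If the sponsor prefers participant counts only, list and justify that in SAP section 14.

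The cost is SAP wording, one extra column per AE table and some programming. The AE records are already collected, and no new test or power statement is needed.

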### **9.1.2. Relationship of Adverse Events to Investigational Medicinal Product**

The investigator will determine whether there is a reasonable causal relationship between the occurrence of the AE and exposure to IMP (FLT201) and non-investigational medicinal products (NIMP) (prednisolone/prednisone, methylprednisolone, and tacrolimus). If there is no valid reason for suggesting a relationship, then the AE should be classified as “Not Related.” Otherwise, if there is any valid reason for suspecting a possible cause-and-effect relationship between the IMP/NIMP and the occurrence of the AE, then the AE should be considered “Related.”

If the relationship to IMP/NIMP information is missing, then the corresponding AE is assumed to be related with reasonable possibility to the IMP/NIMP. If a participant experiences more than one occurrence of the same AE, the occurrence with the most-related relationship to IMP/NIMP will be used in summary tables.

The relationship of AEs to IMP/NIMP will be summarized by SOC, PT, study part, dose cohort, and overall.

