- B If a site is not able to administer FLT201 the Sponsor will attempt to identify an alternative site for the infusion week only.
- C Height (screening only) and weight will also be measured.
- D Vital signs include pulse, blood pressure, respiratory rate, and temperature.
- E Participants will complete BPI-SF questionnaire once a day covering the 7 days following each screening visit, and then for 7 consecutive days, on each occasion commencing at the start of Weeks 4, 12, 24 and 37 post-treatment (week prior to the 38-week visit). Study sites will contact participants at the beginning of Week 37 to remind them to complete the questionnaires during Week 38.
- F Participants will complete the FACIT-Fatigue questionnaires at the end of each week during the screening period, and then at the end of Weeks 4, 12, 24, and 37 post treatment.
- G A weight-based tapering immunosuppressive regimen will be initiated at the Week 3 visit. Cohort 1 may not require immunosuppression. For details see the pharmacy manual.
- H Serum pregnancy test performed only at Week 1 to EOS and unscheduled visits if the urine pregnancy test is positive.
- I Testing to be performed twice weekly (including the testing as part of the scheduled study visit), initially commencing at Week 1 and concluding at the end of Week 9 and later commencing at Week 28 and concluding at the end of Week 38/EOS. The tests should be as evenly spaced through the week as possible, for example: Monday and Thursday, or Tuesday and Friday.
- J Testing to be performed three times weekly (including the testing as part of the scheduled study visit), commencing at Week 10 and concluding at the end of Week 27. The tests should be as evenly spaced through the week as possible, for example Monday, Wednesday, and Friday.
- K Local testing. Weekly CMV PCR testing for the duration the participant is taking tacrolimus in the immunosuppressant regimen. Tests should be undertaken to coincide with use of tacrolimus if outside of the prophylactic regimen. CMV IgG testing followed by CMV PCR. CMV PCR only indicated for a positive CMV IgG.
- L Local testing. Tacrolimus levels should be tested twice weekly until levels are in the therapeutic range and weekly thereafter for the duration the participant is taking tacrolimus in the immunosuppressant regimen. Tests should be undertaken to coincide with use of tacrolimus if outside of the prophylactic regimen.

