10.4 Immunosuppression Management

As noted in Section 6.5.3.1, liver-directed gene therapy with an AAV-based capsid has been reported to be associated with a likely T-cell mediated immune response to vector-transduced hepatocytes resulting in rises in liver transaminase levels, most notably ALT.

For all participants, LFTs will be closely monitored (Section 12.2.1) to enable timely identification and treatment of episodes of breakthrough ALT increase to preserve GCase expression (activity and concentration).

Participants will receive a prophylaxis regimen (post-dosing with FLT201) starting at approximately Week 3 post-dosing, continuing for a duration of up to approximately 3 weeks at the initial dose followed by a taper over 11 to 13 weeks.

The prophylaxis regimen consists of oral steroid (prednisolone/prednisone) and/or oral tacrolimus. An appropriate quantity of steroid and/or tacrolimus will be dispensed to the participant to cover the period between clinic visits and usage will be monitored via tablet counts.

In the event of breakthrough elevation of liver transaminase, participants will be assessed by the treating physician, and a reactive regimen (consisting of IV methylprednisolone) may be initiated in accordance with the CIMP.

The CIMP provides detail of the prophylaxis and reactive regimens, as well as more detailed guidance regarding the assessment and management in case of observed ALT elevation. The CIMP will be available to the investigator, pharmacy, and key study personnel. If the investigator considers that any systemic immune-modifying medication other than those prescribed in accordance with the CIMP may be necessary, this should be discussed with the Medical Monitor and Sponsor.

Any significant changes in the CIMP will be reviewed by the DMC, and changes may be issued as an update to the CIMP and communicated to all sites. If the DMC considers that significant changes are required, such as addition of other drugs (i.e., additional NIMP), then a protocol amendment may also be submitted.

11 Concomitant Medication

All non-study treatment received within 30 days prior to initial informed consent and for the duration of the study must be recorded on the appropriate eCRF page. Concomitant medication includes prescription and non-prescription medication and herbal treatments. Concomitant medication also includes immunosuppressants used as part of an immune management and monitoring regimen as described in the CIMP.

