14.3.3 Serious Adverse Event NIMP Causality Assessment

As per Section 14.2.4, the investigator must make the assessment of causal relationship for any SAE to the NIMP that the participant has received.

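### A missing causality entry is counted as related without checking exposure, so an AE can be tabulated as related to a product the participant had not yet received or never received

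*SAP*

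**What the plan says.** SAP 9.1.2 has the investigator judge each AE against FLT201 and against the NIMPs (prednisolone/prednisone, methylprednisolone, tacrolimus), and supplies a default for blanks: "If the relationship to IMP/NIMP information is missing, then the corresponding AE is assumed to be related with reasonable possibility to the IMP/NIMP". When the same AE recurs in a participant, the occurrence with the strongest relationship goes into the table. The output is defined as follows: "The relationship of AEs to IMP/NIMP will be summarized by SOC, PT, study part, dose cohort, and overall". No exposure or date condition is attached to the default there or elsewhere in the SAP.

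Three features of the design bear on this.

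- **AE collection starts at consent.** SAP 9.1: "This includes events occurring during the screening phase of the study and regardless of whether FLT201 is administered".
- **NIMPs start later and are not uniform.** Protocol 10.4: "Participants will receive a prophylaxis regimen (post-dosing with FLT201) starting at approximately Week 3 post-dosing", and "The prophylaxis regimen consists of oral steroid (prednisolone/prednisone) and/or oral tacrolimus". IV methylprednisolone is only a reactive option for a breakthrough transaminase rise. Footnote G to the Protocol's Table 1 adds: "Cohort 1 may not require immunosuppression".
- **For SAEs, NIMP causality is framed by receipt.** Protocol 14.3.3, which refers back to 14.2.4, says "the investigator must make the assessment of causal relationship for any SAE to the NIMP that the participant has received". Protocol 14.2.4 itself asks for an FLT201 and a NIMP assessment of every AE, without that limit.

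**The concern.** SAP 9.1.2 describes causality as a link between an event and exposure to a product. Where there has been no exposure there is nothing to be related to, yet the default still returns 'related'. The design guarantees such periods: screening for FLT201, roughly the first three weeks after infusion for the NIMPs, and the whole study for any NIMP that a participant never receives.

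The relationship table is where a reader separates what may be due to the vector from what may be due to the immunosuppressants. A NIMP relationship created by a blank field, in someone who had not taken the drug, is a plain error in that table. The most-related rule lets the error spread. A blank for an early, unexposed occurrence becomes 'related' and then displaces a genuine 'Not Related' given for a later, exposed occurrence of the same event. With two or three participants per cohort, nothing dilutes it.

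**Working it through.** The plan attaches no figure to this rule and has no formal sample size calculation, so there is nothing to reproduce. The check is a comparison of texts, followed by simple arithmetic on how much time is unexposed and how much one imputed event weighs.

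**Step 1: the default against the exposure schedule**

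| Situation | Had the product been received? | Result if the relationship is blank |
|---|---|---|
| Screening AE, FLT201 | No | Related to FLT201 |
| AE between infusion and first NIMP dose | No | Related to NIMP |
| Any AE in a Cohort 1 participant given no immunosuppression | Never | Related to NIMP |
| AE in a participant on steroid alone, if causality is recorded per drug | Never had tacrolimus | Related to tacrolimus |
| AE after the first NIMP dose | Yes | Related to NIMP (a reasonable conservative default) |

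Only the last row is what a conservative default is meant to achieve.

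**Step 2: unexposed time**

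Inputs: screening of up to 16 weeks (Protocol 12.1.1), follow-up of 38 weeks (Protocol Synopsis), NIMP start at about Week 3 (Protocol 10.4).

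- Post-dose time before planned NIMP: 3 / 38 = 7.9%.
- With screening at its maximum length: (16 + 3) / (16 + 38) = 19 / 54 = 35%.
- Cohort 1 participant with no immunosuppression: 38 / 38 post-dose weeks.

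The 7.9% is the figure to use. The 35% applies only if screening runs its full length and screening AEs enter the relationship table. SAP 9.1.2 says AEs rather than TEAEs, but Protocol 15.3 places the relationship summary directly after the treatment-emergent frequencies, so the scope is not settled. Time after the planned course ("continuing for a duration of up to approximately 3 weeks at the initial dose followed by a taper over 11 to 13 weeks") is not counted as unexposed, because once a drug has been given a later effect cannot be ruled out.

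The 38 weeks apply outside the US. SAP 7.2.2 gives Month 24 as the end of study for US participants, and the US immunosuppression schedule is not in these documents.

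**Step 3: weight of one imputed participant on one term**

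Inputs: at least 2 participants per cohort with a possible third (Protocol Synopsis), about 12 + 6 = 18 in total (SAP 4.2).

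- Cohort of 2: 1 / 2 = 50 percentage points.
- Cohort of 3: 1 / 3 = 33 percentage points.
- All 18: 1 / 18 = 5.6 percentage points.

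**Step 4: which outputs are touched**

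- Relationship table (SAP 9.1.2): yes.
- AE overview (SAP 9.1.1): its relationship rows count IMP-related TEAEs, so NIMP relationship is not used.
- DLT definitions (SAP Table 9-1): relationship to FLT201 only.

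The expected number of false attributions cannot be computed, because the documents give no rate of missing causality.

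**The case against.** The strongest reply is that a blank should not occur. Protocol 14.2.4 requires an assessment for every AE and directs 'not related' when nothing suggests a link, and SAP 9.1.2 repeats that instruction before giving its default. A drug not taken should therefore produce 'Not Related', and the default is a fallback for data gaps. It is also deliberately conservative, in line with SAP 9.1.3, which sets missing severity to severe. AEs are listed, medications are listed, and immunosuppressant dose is plotted over time, so an impossible attribution could be spotted.

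Much of this stands, and it rules out several stronger readings.

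- A reader might infer from Protocol 14.3.3 that a blank is the proper entry for a NIMP not received. That section covers SAEs only, refers back to 14.2.4, and never says to leave a field empty. A blank is possible, but the documents do not make it correct or expected.
- A reader might infer that vector toxicity would be relabelled as immunosuppressant toxicity. Relationship is assessed for FLT201 and NIMP alike, so an imputed NIMP link stands beside the FLT201 attribution and does not replace it.
- A reader might infer attribution to tacrolimus or methylprednisolone by name. That requires a separate causality field per drug, and the documents do not show whether the eCRF has one or offers 'not applicable'.
- A reader might take 35% as an error rate, or assume that false attributions cluster around the infusion. The 35% is a maximum share of time, and nothing is known about where blanks will fall.

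What the reply does not answer is the rule itself. A fallback written for gaps should behave sensibly when a gap occurs, and this one returns an impossible result for unexposed periods. Listings let a careful reader find the error but do not remove it from the table.

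**Conclusion.** The point holds in a limited form. As written, SAP 9.1.2 would tabulate an AE with a missing relationship as related to a product not yet received or never received, and the most-related rule could let that value override a real investigator assessment. Treating missing as related is a sound convention; the only defect is the absent exposure condition.

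The effect is confined mainly to one descriptive table. Post-dose, it concerns about 7.9% of follow-up under the planned schedule, and all of it for a Cohort 1 participant given no immunosuppression. One such participant shifts a term by 33 points in a cohort of 3. The FLT201 part, for screening AEs, arises only if the table covers all AEs and not just TEAEs.

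The verdict assumes that at least one blank occurs and that prophylaxis starts near Week 3. It does not depend on how the eCRF is built, although the eCRF decides whether the false link is to a named drug or to NIMP in general. The correction is worth making because the rule is wrong on its face and cheap to repair. The documents do not show that the trial's safety conclusions are at risk.

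**What to change.** Replace the default in SAP 9.1.2 with wording such as:

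> A missing relationship is assumed related only for a product the participant had received on or before the onset or any worsening of the AE (FLT201: infusion date; NIMP: actual first dose date in the Immunosuppressant Log, per drug if the eCRF records causality per drug, otherwise any NIMP). If dates are too incomplete to exclude prior exposure, related is assumed. Otherwise the AE is classed as not applicable for that product.

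Three details matter.

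- The worsening clause is needed because an event can begin before a drug and worsen on it, as the TEAE definition in SAP 9.1.1 already recognises. A cut on onset alone would drop such events.
- 'Not applicable' should rank below 'Not Related' when the most-related occurrence is chosen.
- The relationship table should carry a footnote with the number of imputed relationships, and its title should say whether it covers all AEs or TEAEs only.

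The cost is small: a few sentences and one extra date derivation. The log is already in the eCRF with daily dosage (Protocol 10.3), and SAP 7.2.2 already plots immunosuppressant dose over time. The conservative default stays in force wherever exposure occurred or cannot be excluded.
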